5. Determine time required to attain subject understanding of use of Apple Watch

features (steps, stand hours, active calories, exercise minutes, heart rate - resting, walking, variability, flights climbed)

B. Randomized Controlled Trial (RCT) Cohort (Cohort II)

Primary Objective

1. Demonstrate non-inferiority of the study group, when measuring 30-day all cause readmission rates, when compared to the control group who will undergo standard of care education and an outpatient PT regimen.

C. Correlative Analytics Cohort (Cohort III)

In addition to traditional data collection mechanisms, four passive outcome measures will be captured among all mymobility study subjects via the Apple Watch sensors in combination with the mymobility App, attempting to develop correlative measures to assist surgeons in understanding and managing risk in their patient populations. These correlative outcomes will be measured using steps, stand hours, active calories, exercise minutes, heart rate (average, resting, walking, and variability), and flights climbed that will be analyzed in statistical models (including multivariate regression models). Details and methodology are provided in **Section XVI**.

Primary Objectives

1. Assess the differences in episode of care data compiled, collected, and delivered in the mymobility platform to correlate the incidence of the seven most common post TJR medical complications (UTI, ileus, MI, pneumonia, DVT/PE, prolonged wound drainage, wound infection).
2. Assess the ability of preoperative and episode of care data compiled, collected, and delivered in the mymobility application (from, among other sources, the Apple Watch sensor platform) to correlate with discharge disposition (home vs. non-home - ACF or SNF)
3. Identify 90-day mymobility data points which correlate with 30-day post op ROM data (90 degrees of flexion) within the TKA and PKA populations.
4. Assess the ability of postoperative data compiled, collected, and delivered in the mymobility application (from, among other sources, the Apple Watch sensor platform) collected during postoperative days 0-90 to predict which subjects will have a “very satisfied” or “satisfied” score on the Patient Satisfaction component of Patient Questionnaire #3 at 90 days.

Secondary Objectives

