The Informed Consent process may be completed in-person or through an IRB/EC approved remote method. After completing the Informed Consent process, candidates who agree to enter the study must sign and date the IRB/EC approved ICF. The ICF must be signed and dated prior to onboarding. Study data will not be collected until the ICF has been signed and dated. If the candidate does not wish to participate (does not sign and date the ICF), data for that candidate will not be collected for this study.

A copy of the signed and dated ICF must be provided to the study subject. The original signed and dated ICF is to be filed in the subject's medical record, study subject binder, or regulatory binder.

D. Subject Enrollment

Once the ICF has been signed and dated by the subject, the subject will be considered enrolled in the study. A unique subject identification number (Subject ID) will be assigned to each participating subject.

This unique Subject ID number will be used throughout the study for identification. The subject will be considered an active study subject after receiving training in the appropriate use, participation and functionality of the mymobility platform and Apple Watch. In the event that the subject does not undergo knee or hip arthroplasty as outlined in the inclusion criteria, the subject will be considered a screen failure and a **Study Completion Form** will be used to document the subject's exit from the study.

E. Baseline/Preoperative Assessment

The following baseline/pre-operative data will be collected at the time of enrollment:

1. Inclusion/Exclusion Criteria
 - a. Randomization (RCT cohort only, recorded in EDC)
2. Demographics & History Form
3. Pre-op Physical Exam
 - a. Knee/Hip specific assessments including ROM

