The RCT cohort will include 1,000 subjects. This is based on the sample size of 794 required to show non-inferiority on the readmission rate endpoint. Accounting conservatively for 20% Loss-to-follow-up, 1,000 subjects will ensure the study is adequately powered. This study is powered appropriately to show non-inferiority between the mymobility group and control group.

- i. This study is designed to show that the mymobility group is non-inferior to the control group using one primary study endpoint. This will be shown using a closed testing method in which the primary endpoint of readmission rate is compared using $\alpha=0.05$. Study success requires that the study group successfully demonstrates non-inferiority on this end point using the statistical methods described.

2. Apple Watch/mymobility Correlative Analytics

Although there is no well-defined method to calculate the power of a predictive model before it has been developed, the low rate of certain outcomes such as manipulation under anesthesia, readmission, embolism, etc. will increase the number of subjects needed to create a reliably predictive tool that could be used to correlate events and data in order to make claims in clinical decision making. Generally, very large numbers are required to demonstrate predictive power for a predictive statistical model. A goal of 10,000 subjects has been set, with interim analyses at 2,500, 5,000 and 7,500 subjects to determine continued need for subject enrollment. Assuming a complication rate of ~3% and a discharge rate of ~5% to postoperative rehab facility in the study population of 10,000 subjects in the Correlative Analytics Cohort, this implies that 300 subjects will have some type of complication and 500 subjects will be discharged to a rehab facility. Given the fact that our goals are to identify high positive predictive value and area under the curve (AUC) upper and lower threshold values of Apple Watch measured and transmitted biometric data (steps, stand hours, active calories, exercise minutes, heart rate - resting, walking, variability, flights climbed), using multivariate regression to correlate with post-op complications, and risks of discharge to rehab facility, we would conclude that a Predictive Signatures Study group of at least 10,000 subjects will be required.

Examples of other studies in the total joint literature that have used multivariate regression models to provide clinically useful cutoff values are provided below:

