- i. Study #1 – Assessing patients for joint replacement; Can pre-operative Oxford hip and knee scores be used to predict patient satisfaction following joint replacement surgery and to guide patient selection?³²
 - N = 3307 subjects
 - In this study, even having an N of 3307 study subjects was not sufficient to produce receiver operating characteristics (ROC) model that was able to predict satisfaction after THA.
- ii. Study #2 – The use of receiver operating characteristics analysis in determining erythrocyte sedimentation rate and C-reactive protein levels in diagnosing periprosthetic infection prior to revision total hip arthroplasty.³³
 - N = 479 subjects

- In this study, a population of 479 who had an infection (analogous to our population of 300-500 subjects who either has some type of complication or is discharged to a rehab facility) was required to produce lower limit threshold values of C-reactive protein and erythrocyte sedimentation rate to diagnose infection.
- iii. Study #3 – Relation between surgeon volume and risk of complications after total hip arthroplasty: propensity score matched cohort study.³⁴
- N = 37,881 subjects
 - In this study, a population of ~38,000 subjects (with approximate complication rate of 2%) was required to create a received operator curve with high PPV threshold values of number of hospital and surgeon cases required to minimize risk of complications after THA.

Based on this sampling of high quality predictive and risk-modeling studies from the TJA literature, we conclude that a study population of at least 10,000 subjects is required to produce clinically useful predictive ROC curves and high PPV threshold values for passively measured Apple Watch measured and transmitted physiologic metrics. As noted earlier, interim analyses will be performed at 2,500, 5,000 and 7,500 subjects to determine emerging heuristics related to complication predictions.

XVII. Quality Control & Quality Assurance

The Investigator will be required to permit representative(s) of the Sponsor's monitoring team to inspect all Case Report Forms and corresponding sections of the study patients office records and/or hospital original medical records. These audits will be done for quality assurance purposes, i.e. verifying adherence to the Clinical Investigation Plan and the completeness and accuracy of the data being entered on the Case Report Forms.

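### Cohort III aims at cut-offs on Apple Watch metrics for complications and discharge, but no analysis compares prediction with and without the watch, so it cannot show what the watch adds to pre-operative risk data already collected.

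*Combined protocol and SAP*

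**What the plan says.** Section VI.C describes the Correlative Analytics Cohort as "attempting to develop correlative measures to assist surgeons in understanding and managing risk in their patient populations". It lists the watch variables, says they will enter statistical models that include multivariate regression, and refers to Section XVI for the methodology.

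Section XVI.C.2 gives the size: "A goal of 10,000 subjects has been set, with interim analyses at 2,500, 5,000 and 7,500 subjects". It justifies this by expected events: "Assuming a complication rate of ~3% and a discharge rate of ~5% to postoperative rehab facility", so that "300 subjects will have some type of complication and 500 subjects will be discharged to a rehab facility". The goal is to "identify high positive predictive value and area under the curve (AUC) upper and lower threshold values of Apple Watch measured and transmitted biometric data", "using multivariate regression to correlate with post-op complications, and risks of discharge to rehab facility". The section closes by restating the product as predictive ROC curves and "high PPV threshold values for passively measured Apple Watch measured and transmitted physiologic metrics".

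Baseline information appears elsewhere:

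- Section X.E collects the "Demographics & History Form", a physical exam with ROM, EQ-5D-5L and KOOS, JR. or HOOS, JR. before surgery.
- Section XII.B says comorbidities may come from OrthoVal at selected US sites in place of manual chart review.
- Section VI.C, primary objective 2 (discharge disposition), uses pre-operative as well as episode-of-care data, with the watch as one source among several.
- Section VI.C, secondary objectives, mentions patient attributes and surgical technique, and gives as an example grouping by age and BMI before relating watch data to outcome.
- Section XVI.A plans exploratory models relating demographics, adherence, HealthKit data and outcomes.

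No section gives a covariate list for the Cohort III models, a baseline-only comparator, a criterion for added value, a significance level, or a target AUC or PPV.

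**The concern.** The cohort is meant to help surgeons manage risk, and a surgeon already has the pre-operative chart. The useful question is whether the watch improves on it. An AUC or PPV for a watch cut-off, with nothing to compare it to, does not answer that question. A patient's activity may partly reflect age, BMI, comorbidity or procedure. If it does, a metric that merely mirrors those factors will be associated with the outcome. External validation would not expose this, because a proxy replicates wherever the underlying association does.

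Putting pre-operative and watch data into one model, as the discharge objective allows, does not settle it either: the joint performance does not separate the watch's share. What is at stake is the use of the results. Section V (purpose 5) lists risk stratification among the intended product uses, and the secondary objectives in Section VI.C say that statistically valid correlations would enable product features.

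**Working it through.** **1. The plan's own figures.** 10,000 × 0.03 = 300 complications and 10,000 × 0.05 = 500 discharges to a rehab facility. Both reproduce exactly. Cohort III has no stated power to reproduce.

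**2. Inputs.** From Section XVI.C.2: N = 10,000, with 300 or 500 events. Assumed, because the documents are silent: a pre-operative risk score X with AUC 0.55-0.70; a watch metric W with correlation ρ = 0.1-0.6 with X and no effect on outcome given X; a two-sided test at 0.05 on one metric; a normal score and metric; baseline risk measured without error; no missing watch data.

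**3. AUC of the proxy metric.** Under the binormal model, AUC(W) = Φ(ρ × z), where z = Φ⁻¹(AUC of X). For AUC(X) = 0.65, z = 0.385. With ρ = 0.3, AUC(W) = Φ(0.116) = 0.546.

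**4. Chance of nominal significance, unadjusted.** With m events and n non-events, the null standard error is √[(m + n + 1)/(12mn)] = √[10,001/(12 × 300 × 9,700)] = 0.0169. The Hanley-McNeil standard error at AUC 0.546 is 0.0173. Power ≈ Φ[(0.046 − 1.96 × 0.0169)/0.0173] = Φ(0.74) = 77%. The same formula elsewhere gives:

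| Events | Baseline AUC | ρ = 0.1 | ρ = 0.3 | ρ = 0.5 |
|---|---|---|---|---|
| 300 | 0.55 | 6% | 15% | 32% |
| 300 | 0.60 | 9% | 43% | 84% |
| 300 | 0.65 | 15% | 77% | 99% |
| 300 | 0.70 | 24% | 95% | 100% |
| 500 | 0.60 | 12% | 63% | 96% |
| 500 | 0.65 | 22% | 93% | 100% |
| 500 | 0.70 | 35% | 100% | 100% |

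Logistic simulation at N = 10,000 agrees. At 300 events, AUC 0.65 and ρ = 0.3, runs of the simulation gave 76-81%. The other three corners of AUC 0.65-0.70 and ρ = 0.3-0.5 gave 95-100%.

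**5. The same metric with X in the model.** It was significant in 3-7% of simulated studies in every scenario tried, which is the nominal 5% within simulation error.

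**6. PPV of the proxy.** A cut-off at the worst tenth of W had a PPV of 3.2-5.3% at a 3% event rate, and 5.4-8.6% at a 5% rate (baseline AUC 0.60-0.70, ρ = 0.1-0.5). The AUC of W was 0.51-0.60.

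**7. Sensitivity.** For AUC 0.65 and ρ = 0.3: 28% at the first interim analysis (2,500 subjects, 75 complications), and 49% at 300 events with a Bonferroni correction for eight metrics.

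**The case against.** The strongest reply is that the plan does not propose an unadjusted analysis. It says multivariate regression, the discharge objective includes pre-operative data, and demographics and age/BMI groups are mentioned. This stands. A reader might infer that watch metrics will be analysed alone, or that a watch threshold can never allow for baseline risk. The documents support neither reading: the covariates are unspecified, and thresholds could be set within strata. What remains is that no passage sets a model with the watch against one without it.

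Second, a reader might infer that a pure proxy would satisfy the plan's criteria. It would not clearly do so. The stated aim is high PPV, and at a PPV of at most 5.3% at least 94.7% of flagged patients would have no complication. Nominal significance is not a Cohort III criterion in the plan. The limit on this reply is that no numerical PPV or AUC target is given, so nothing written would reject a weak metric.

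Third, the size depends on two inputs the documents do not give. That also stands, and the full range has to be shown. What does not depend on them is the return to about 5% after adjustment.

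Finally, the threshold wording covers only complications and discharge, not ROM or satisfaction, and a simple activity flag could be useful for monitoring even if it is partly a proxy. Both points limit the remedy.

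**Conclusion.** The point holds in this form: Section XVI.C.2 makes watch-metric thresholds the product for complications and discharge to a rehab facility, and specifies no comparison that would show their value beyond pre-operative data already collected. The size is conditional. At 300 events, a metric with no added information would be nominally significant unadjusted in about 76-100% of studies if ρ is 0.3-0.5 and the baseline AUC is 0.65-0.70. Over ρ = 0.1-0.6 and baseline AUC from 0.55 upward the range is about 6-100%. With baseline risk in the model it is about 5%. These percentages illustrate the mechanism; they are not error rates of this plan, and they do not imply that a proxy would reach high PPV. The change should be made, but it concerns the cohort's interpretation and does not touch the RCT primary endpoint.

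**What to change.** In Section XVI.C.2, for complications and discharge disposition:

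1. Fit a baseline model from pre-operative data already collected: demographics and history (age, sex, BMI and comorbidities where recorded), procedure, pre-operative KOOS, JR. or HOOS, JR., EQ-5D-5L and ROM.
2. Add the watch metrics as continuous terms.
3. Judge the watch by the likelihood-ratio test and by the change in AUC and in PPV over the baseline model, with confidence intervals.
4. Report cut-offs on the combined predicted risk. Any cut-off on a raw watch metric should be shown alongside the baseline model's performance.

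The cost is plan wording and modest extra programming, with no added visits or patient burden. The worksheets in Appendix 1 are not part of the text reviewed, so the exact fields on the history form should be confirmed before the covariates are fixed. The downside for the sponsor is that reported watch performance will look smaller.
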